5.7.2. Adjustment for Multiple Comparison

The overall type I error will be controlled in each of seronegative mFAS-A and seronegative mFAS-B independently at 2-sided 5% significance level.

Seronegative mFAS-A Subjects

The overall type I error will be controlled for the primary hypothesis in Cohort A based on a 2-sided test at an alpha level of 0.05 as follows:

H0: There is no treatment difference between REGN10933+REGN10987 and placebo in the proportion of subjects with a symptomatic RT-qPCR confirmed SARS-CoV-2 infection during the EAP.

H1: There is a treatment difference between REGN10933+REGN10987 and placebo in the proportion of subjects with a symptomatic RT-qPCR confirmed SARS-CoV-2 infection during the EAP

If the primary efficacy endpoint in Cohort A is statistically significant, the alpha level of 0.05 will be released for the key secondary endpoints in Cohort A. The hierarchy testing sequence of key secondary endpoints is presented in the following table.

Table 2: Hierarchy Testing Sequence of Key Secondary Efficacy Endpoints in Seronegative mFAS-A

Key Secondary Efficacy Variables
Proportion of subjects with viral load >4 (log10 copies/mL) in NP swab samples during the EAP
Number of weeks of symptomatic RT-qPCR confirmed SARS-CoV-2 infection (broad-term) during the EAP
Number of weeks of high-viral load >4 (log10 copies/mL) in NP swab samples during the EAP
Number of weeks of RT-qPCR confirmed SARS-CoV-2 infection (regardless of symptoms) during the EAP
Proportion of subjects who have a RT-qPCR confirmed SARS-CoV-2 infection (regardless of symptoms) during the EAP
Proportion of subjects in placebo group with a RT-qPCR confirmed SARS-CoV-2 infection during the EAP with an index case participating in study R10933-10987-COV-2067 (comparison of those whose index cases receive REGN10933+REGN10987 vs placebo in R10933-10987-COV-2067)

Seronegative mFAS-B Subjects

The overall type I error will be controlled for the primary hypothesis in Cohort B based on a 2-sided test at an alpha level of 0.05 as follows:

H0: There is no treatment difference between REGN10933+REGN10987 and placebo in the proportion of subjects who subsequently develop signs and symptoms (broad-term) within 14 days of a positive RT-qPCR at baseline or during the EAP

H1: There is a treatment difference between REGN10933+REGN10987 and placebo in the proportion of subjects who subsequently develop signs and symptoms (broad-term) within 14 days of a positive RT-qPCR at baseline or during the EAP

If statistical significance is established for the primary efficacy endpoint in cohort B, a hierarchical testing procedure will be applied to the key secondary endpoints in Cohort B at a 2-sided 0.05 significance level. The order of testing sequence for key secondary endpoints is presented in the following table.

Table 3: Hierarchy Testing Sequence of Key Secondary Efficacy Endpoints in Seronegative mFAS-B

Key Secondary Efficacy Variables
Number of weeks of symptomatic SARS-CoV-2 infection (broad-term) within 14 days of a positive RT-qPCR at baseline or during the EAP
Number of weeks of high viral load (\log_{10} copies/mL) >4 in NP swab samples during the EAP

5.7.3. Analyses of Key Secondary Variables

For Cohort A, the key binary endpoint of the proportion of subjects who have a RT-qPCR confirmed SARS-CoV-2 infection (regardless of symptoms) during the EAP, the same statistical method used in the primary analysis will be applied. If a subject's overall infection status during the EAP cannot be determined due to missing RT-qPCR results, the following rules will be applied to impute the missing RT-qPCR data.

1. For subjects satisfying the criteria specified in the handling missing central lab SARS-CoV-2 RT-qPCR data of the analysis of primary efficacy variables, the corresponding visit(s) will be considered as having a positive RT-qPCR test.
2. After the first step above, each planned visit with missing RT-qPCR data will be imputed 100 times to generate 100 complete datasets based on the predicted probability using the fully conditional specification (FCS) ([Van Buuren, S, 2005](#))^[7] through the logistic regression. The logistic regression model includes the fixed effect factors of treatment group, region, age group, and RT-qPCR testing status at other analysis visits during the EAP. This imputation will repeat by iterating for each analysis visit with missing RT-qPCR testing status. Appendix [10.4](#) provides details on the use of FCS from the SAS MI procedure. These 100 complete datasets will be analyzed using the model specified above for the primary analysis. Results from 100 analyses will be combined using Rubin's formulae to obtain the final estimate of $\log(\text{odds ratio})$, 95% CI and the associated p-value. The odds ratio and 95% CI will be derived by taking the exponential of these estimates.

For the key binary endpoint of the proportion of subjects with viral load >4 (\log_{10} copies/mL), if NP swab viral load data is missing for a visit, it will not be imputed regardless of symptoms. Only non-missing available NP swab viral load data will be used for the analysis of this endpoint. Only subjects with at least one post-baseline viral load (\log_{10} copies/mL) data in NP swab samples will be included in the analysis.

For Cohort A the key binary endpoint regarding the index case linkage to R10933-10987-COV-2067, the Fisher's exact test will be used.

For continuous key secondary endpoints in Cohort A and Cohort B (e.g., number of weeks of high viral load >4 (\log_{10} copies/mL) in NP swab samples and number of weeks of symptomatic RT-qPCR-confirmed SARS-CoV-2 infection (broad-term) during the EAP, etc.), visits with missing viral load regardless of symptoms and visits with missing RT-qPCR that do not have any broad-term symptoms within 14 days will not be considered as meeting these endpoint criteria, respectively. For endpoints regarding viral load, only subjects with at least one post-baseline data

will be included in the analysis. These endpoints will be analyzed by the non-parametric method, a stratified Wilcoxon rank sum test (Van Elteren Test) with the region and age group. Descriptive statistics will be provided for number (%) of subjects with each interval of duration in weeks (i.e., 0 week, > 0 to \leq 1 week, > 1 to \leq 2 weeks, etc.) within each treatment group. The total weeks of infection and normalized duration (e.g., average duration infection per 1000 subjects) per treatment group will also be reported.

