## 8.8. Concomitant Medications and Procedures

Any treatment administered from the single dose of study drug to final study visit will be considered concomitant medication. This includes medications that were started before the study and are ongoing during the study.

As per Section 6.1.4 and Section 6.1.5, a positive SARS-CoV-2 test which is associated with a symptomatic SARS-CoV-2 infection and is conducted in a local laboratory associated with a medical facility, should be recorded as a concomitant procedure and associated with the COVID-19 AE.

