#### 11.4.3.2. Key Secondary Efficacy Analyses

For cohort A, the key binary endpoint of the proportion of subjects who have a RT-qPCR confirmed SARS-CoV-2 infection (regardless of symptoms) during the EAP, the same statistical method used in the primary analysis will be applied. If a subject's overall infection status during the EAP cannot be determined due to missing RT-qPCR results, the following rules will be applied to impute the missing RT-qPCR data.

1. For subjects satisfying the criteria specified in the handling of missing central lab SARS-CoV-2 RT-qPCR data of the analysis of primary efficacy variables, the corresponding visit(s) will be considered as having a positive RT-qPCR test.
2. After the first step above, each planned visit with missing RT-qPCR data will be imputed 100 times to generate 100 complete datasets based on the predicted probability using the fully conditional specification (FCS) ([Van Buuren, 2006](#)) through the logistic regression. The logistic regression model includes the fixed effect factors of treatment group, region, age group, and RT-qPCR testing status at other analysis visits during the EAP. This imputation will repeat by iterating for each analysis visit with missing RT-qPCR testing status. Full details on details on the use of FCS from the SAS MI procedure will be provided in the SAP.

For the key binary endpoint of the proportion of subjects with viral load  $>4$  (log10 copies/mL), if NP swab viral load data is missing for a visit, it will not be imputed regardless of symptoms. Only non-missing available NP swab viral load data will be used for the analysis of this endpoint. Only subjects with at least one post-baseline viral load (log10 copies/mL) data in NP swab samples will be included in the analysis.

For cohort A the key binary endpoint regarding the index case linkage to R10933-10987-COV-2067, the Fisher's exact test will be used.

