4.5.2. Cohort A Key Secondary Efficacy Variables

The key secondary efficacy variables listed below include two types of variables: binary (B) and continuous (C) variables.

Key Secondary Efficacy Variables	Type	Cohort A
Proportion of subjects with viral load >4 (log ₁₀ copies/mL) in NP swab samples during the EAP	B	X
Number of weeks of symptomatic RT-qPCR confirmed SARS-CoV-2 infection (broad-term) during the EAP	C	X
Number of weeks of high viral load >4 (log ₁₀ copies/mL) in NP swab samples during the EAP	C	X
Number of weeks of RT-qPCR confirmed SARS-CoV-2 infection (regardless of symptoms) during the EAP	C	X
Proportion of subjects who have a RT-qPCR confirmed SARS-CoV-2 infection (regardless of symptoms) during the EAP	B	X
Proportion of subjects in placebo group with a RT-qPCR confirmed SARS-CoV-2 infection during the EAP with an index case participating in Study R10933-10987-COV-2067 (comparison of those whose index cases receive REGN10933+REGN10987 vs placebo in Study R1033-10987-COV-2067)	C	X

Duration of symptomatic infection (weeks) is defined as (the end date of all symptoms minus the date of the first symptom+1)/7, where a symptom is defined in Section 4.5. If the symptom is ongoing at the time of the first step analysis, the end date of the symptom will be set as the cutoff date for the first step analysis.

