In Cohort B, a subject will be considered having a symptomatic RT-qPCR confirmed SARS-CoV-2 infection (broad-term) during the EAP if subjects have at least one symptom within 14 days of a positive RT-qPCR result at baseline or during the EAP.

Handling of Missing Central Lab SAR-CoV-2 RT-qPCR Data for Both Cohort A and Cohort B

Subjects with COVID-19 symptoms that are missing a central lab determined RT-qPCR test during the EAP (eg. are too sick to go to the study site) but have a positive SARS-CoV-2 test from a local lab (eg. in the hospital) will be considered as having a symptomatic infection if any of the symptoms occurred within 14 days of the positive SARS-CoV-2 test that was observed during the EAP.

The graphical display using Kaplan-Meier curve for the time to first symptom will also be provided.

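### For the cohort A key secondary on infection regardless of symptoms, a positive local test stands in for a missing central PCR only when the subject had symptoms, which biases the endpoint slightly toward the arm with fewer symptoms

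*SAP*

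**What the plan says.** The endpoint is fifth in the cohort A hierarchy (SAP 5.7.2, Table 2; protocol Table 10). SAP 4.5.2 defines it as "Proportion of subjects who have a RT-qPCR confirmed SARS-CoV-2 infection (regardless of symptoms) during the EAP". Imputation starts only where a subject's "overall infection status during the EAP cannot be determined due to missing RT-qPCR results" (SAP 5.7.3).

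**Step 1.** The SAP text opens "For subjects satisfying the criteria specified in the handling missing central lab SARS-CoV-2 RT-qPCR data of the analysis of primary efficacy variables", and protocol 11.4.3.2 gives the consequence: "the corresponding visit(s) will be considered as having a positive RT-qPCR test". The borrowed criteria are in SAP 5.7.1. They cover "Subjects with COVID-19 symptoms that are missing a central lab determined RT-qPCR test during the EAP" who also have a positive local result. Such a subject "will be considered as having a symptomatic infection if any of the symptoms occurred within 14 days of the positive SARS-CoV-2 test". Symptoms are required to enter the rule and again for its timing condition.

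**Step 2.** Every visit still missing is imputed 100 times by fully conditional logistic regression. The predictors are treatment, region, age group and PCR status at the other visits; the code in SAP Appendix 10.4 has the same list. Neither symptoms nor a local result is a predictor.

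**Collection.** Protocol 8.8 asks sites to record "a positive SARS-CoV-2 test which is associated with a symptomatic SARS-CoV-2 infection and is conducted in a local laboratory". Protocol 6.1.4 asks for all outside assays, but only for subjects hospitalised with suspected COVID-19.

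**A competing rule.** SAP Appendix 10.1 words the primary-endpoint rule differently: symptoms near a visit with missing PCR are enough, and no local test is mentioned.

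**The concern.** Take two infected subjects, each with the relevant central swab missing, no other central positive, and a positive local test. The one with symptoms is counted as infected. The one without is handed to a model that does not know about the positive test. For an endpoint that is meant to disregard symptoms, that is a contradiction in the rule itself.

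It matters because the arms are expected to differ in symptoms. In the administrative assessment (protocol 3.2.5), symptomatic infection occurred in 8/223 placebo and 0/186 active subjects. Step 1 would therefore rescue roughly a third of local-only infections on placebo and almost none on active. The endpoint is tested under alpha control, and first-step results may go into a submission (SAP 7). The two sensitivity analyses in SAP 5.7.1.1 concern infections within 72 hours of dosing and non-GCP-compliant sites, both for the primary endpoint, so neither would expose this.

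**Working it through.** **The plan's own figures.** The documents give no figure for this rule or for power on this endpoint. The general planning figures reproduce. With 624 per arm and 10% v 5%, a two-proportion normal approximation gives power 0.919, against 0.914 in SAP Table 1 at within-household correlation 0.1. And 1248 / 0.9 / 0.7 = 1981, against the stated 1980.

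**How often step 2 calls such a subject positive.** Step 2 was simulated over four weekly visits (60,000 subjects per setting, 3 imputations, visit pattern assumed). Asymptomatic local positives came out positive about 2% to 5% of the time. Below, q is this probability.

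**Inputs.**
- s, share of infections with symptoms. Protocol 3.2.6 gives 21 infected placebo and 9 infected active subjects in its viral-load comparison. Its day-8 rate of 10.3% implies about 23 of 223 on placebo. So s on placebo is 8/21 = 38% or 8/23 = 35%. On active it is 0.
- u, share of infections with no positive central swab but a positive local test. It is not in the documents; 5%, 10% and 20% are assumed, equal in both arms.

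**Formula.** Measured rate = I × [(1 − u) + u × (s + (1 − s) × q)], where I is the true infection rate. The fraction of infections lost is u(1 − s)(1 − q).

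**No true effect on infection (I equal in both arms), s = 8/21 v 0, q = 0.05.** Lost on placebo: u × 0.619 × 0.95 = 0.588u. Lost on active: 0.95u.
- u = 5%: (1 − 0.0475) / (1 − 0.0294) = 0.98
- u = 10%: (1 − 0.095) / (1 − 0.0588) = 0.96
- u = 20%: (1 − 0.19) / (1 − 0.1176) = 0.92

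**False-positive rate.** With I = 10% in both arms, 624 per arm, s = 8/23 v 0, q = 0.03, and household correlation ignored (2.5% is nominal in the drug's favour):

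| u | Null RR | Difference in events per 624 | Chance of a false result favouring the drug |
|---|---|---|---|
| 2% | 0.993 | 0.4 | 2.7% |
| 5% | 0.983 | 1.1 | 3.2% |
| 10% | 0.964 | 2.1 | 4.0% |
| 20% | 0.923 | 4.2 | 6.3% |
| 50% | 0.753 | 10.5 | 24% |

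**Other symptom shares at u = 5%, 10%, 20%.** 60% v 0%: RR 0.970, 0.939, 0.874. 50% v 25%: RR 0.988, 0.975, 0.946.

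**With the administrative effect.** The true RR is (9/186) / (21/223) = 0.514. Multiplying by the ratios above gives 0.504, 0.494 and 0.472.

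**After the change.** If every local positive counts, the measured rate returns to I in both arms and the null RR is 1 (simulated odds ratios 0.98 to 1.02, which is noise). This requires local positives to be on file regardless of symptoms.

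**The case against.** **Few subjects can be affected.** Every subject has a weekly central swab whether or not symptomatic (protocol 9.1.1, footnote 17). PCR positivity is said to last 7 to 28 days (protocol 3.2.6). Suspected infection prompts an extra central swab (protocol 6.1.4). One central positive settles the subject's status. The example given for a missed swab with a local positive is being too ill to attend, which does not describe an asymptomatic subject. If only 1% or 2% of asymptomatic infections are local-only (assumed), the formula gives a null RR of 0.996 or 0.993. This largely stands. It is weakened by protocol 3.2.6, which reports that active-arm infections lasted no more than one week while about 40% of placebo infections lasted three to four weeks. One missed swab can hide the former more easily. If u were 10% on active and 5% on placebo, the null RR would be 0.905 / 0.971 = 0.93; at 20% and 10% it would be 0.81 / 0.941 = 0.86. These shares are also assumptions.

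**The endpoint is PCR-confirmed.** SAP 4.5 bases PCR results on the central laboratory, so asking for symptoms before trusting an outside test is a defensible specificity choice. Accepting no local tests would indeed be coherent. Accepting them according to symptoms is not, for an endpoint that disregards symptoms.

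**Changing the rule alone recovers little.** Protocol 8.8 asks for local positives only when tied to symptomatic infection, and outside testing is itself likely to follow symptoms. Protocol 11.4.9 describes EAP data for subjects randomised by 28 January 2021 as already collected, so a revised 8.8 cannot help them prospectively. This stands and shapes the fix.

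**Conclusion.** The rule contradicts its own endpoint, and the direction of the bias is clear: it favours the arm with fewer symptoms. The size is probably small. At an assumed local-only share of 5% to 10%, the null RR is about 0.98 to 0.96 and the chance of a false result in the drug's favour rises from 2.5% to about 3% to 4%. Visible distortion needs roughly 20% or more, or clearly unequal shares between arms. The result rests on the assumed u, on symptom shares from a small administrative sample, on q of 2% to 5%, and on ignoring household correlation.

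A reader might infer that a drug that only suppresses symptoms would be declared to prevent infection. The documents do not support that. The bias is too small at plausible shares. The hierarchy also tests the proportion with high viral load first and weeks of high viral load third. Both use central nasopharyngeal data with no imputation and no local tests, so such a drug should ordinarily stop there. Nor is this the only controlled endpoint bearing on infection: the fourth, weeks of infection regardless of symptoms, includes subjects with zero weeks.

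**What to change.** 1. In SAP 5.7.3 step 1 and protocol 11.4.3.2, for this endpoint only, count a visit with a missing central result as positive if there is any positive local SARS-CoV-2 test in the EAP, with or without symptoms. Keep the symptom condition for the primary endpoint.
2. Before unblinding, query sites for local positives regardless of symptoms. The asymptomatic COVID-19 adverse events tabulated under SAP 5.8.1 are a starting point. Align protocol 8.8 with this.
3. Report by arm how many subjects step 1 reclassifies.
4. Add a sensitivity analysis that uses central PCR only.
5. Reconcile SAP Appendix 10.1 with SAP 5.7.1, so that it is clear whether symptoms alone can turn a missing PCR positive.

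The text changes are short and the added analyses light. The real cost is the site query. The downside is a few events from less standardised tests, which the plan already accepts for symptomatic cases, and some residual bias if outside testing is itself driven by symptoms. Items 3 and 4 would show whether that matters.

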### 3.2.2. Subject Population

The study population will consist of approximately 3500 adult and adolescent subjects and approximately 250 pediatric subjects <12 years old, with household contact exposure to individual with a confirmed SARS-CoV-2 infection. In this study, the household contact must share the same residence and have a close exposure to the first individual in the household with a known SARS-CoV-2 infection (index case). In the case where more than 1 index case is the first known SARS-CoV-2 infected individual in the household (eg, 2 people are tested at the same time), this is allowed, and 1 index case should be chosen, at the discretion of the investigator, to be labeled “index case” in the household CRF. The study was originally planned to enroll 2000 adult and adolescent subjects. However, a blinded analysis of approximately 25% of enrolled subjects in this study was performed, demonstrating that higher than expected seropositivity was observed in cohort A. Therefore amendment 4 for the protocol increased the sample size for the study to account for the higher than expected seropositivity in cohort A. Amendment 5 for the protocol increased the sample size further to accommodate the administrative assessment of assumption verification and sample size estimation.

A household is defined as a group of people who live together at the same residence and share multiple living spaces (eg, living room, bedroom, kitchen, bathroom). In case there is uncertainty that the characteristics of the residence meets the definition of a ‘household’, the investigator and the Regeneron Medical Monitor should discuss prior to randomization.

To be included in the study, subjects must be randomized within 96 hours of collection of the index cases’ positive SARS-CoV-2 diagnostic test sample. Household contacts of individuals infected with SARS-CoV-2 are at a high risk for acquiring infection, with transmission rates ranging from approximately 10% to 15% in these settings (Burke, 2020) (Jing, 2020) (Li, 2020b). Therefore,

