2.2. Sample Size and Power Considerations

2.2.1. Cohort A

The primary hypothesis is the reduction in the proportion of symptomatic RT-qPCR (broad-term) confirmed SARS-CoV-2 infections in seronegative subjects. To calculate the sample size to achieve at least 90% power for seronegative subjects in cohort A, it is assumed that the statistical hypothesis will be tested in a 2-sided test. Based on the administrative assessment results among 409 seronegative subjects in cohort A, an approximately 50% reduction of infection (symptomatic or asymptomatic) compared to placebo group and a 100% reduction of symptomatic infection compared to placebo group was observed. Due to the small sample size in the administrative assessment, it was assumed, for the purpose of assessing study power, that an approximately 50% reduction or greater in symptomatic infections compared to the placebo group will be expected for the final primary efficacy analysis.

In this household study design, the number of subjects per household, the correlation between subjects and symptomatic infection rates within a household are unknown. To detect a relative risk of 0.5 (i.e., 50% reduction of the assumed 10% attack rate in the placebo arm), equivalent to an odds ratio of 0.47, power was calculated compared to the p-value of 0.05 based on 2000

simulations in 1248 subjects from 430 households (i.e., assuming an average household size of 2.9 seronegative subjects). **Table 1** provides power calculations by varying degrees of correlation within household. In all cases, the power of the study is >90% using a generalized linear model with the generalized estimation equation (GEE) approach assuming a compound symmetry covariance matrix.

Table 1: Simulated Power for Household Design (1248 Subjects over 430 Households)

Placebo Attack Rate	REGN10933+ REGN10987 Attack Rate	Correlation within Household	Average Odds Ratio REGN10933+REGN10987 versus Placebo	Power
10%	5%	0.1	0.485	0.914
10%	5%	0.2	0.485	0.934
10%	5%	0.3	0.480	0.956
10%	5%	0.4	0.481	0.972
10%	5%	0.5	0.476	0.983
10%	5%	0.6	0.478	0.999

At least 1980 subjects will need to be enrolled in cohort A to have a minimum of 1248 seronegative subjects, assuming that 10% of subjects drop out, and 30% of subjects are seropositive at baseline.

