5.7.1. Analysis of Primary Efficacy Variables

Cohort A

The Cohort A primary efficacy endpoint described in Section 4.5.1 will be analyzed in the seronegative mFAS-A population. All post-baseline efficacy assessments obtained in the EAP will be included for the primary analysis.

In order to account for the correlation among subjects within a household and control the associated type 1 error inflation, a generalized linear model will be used to estimate the odds ratio between the treatment groups by using the GEE approach (See Appendix 10.4 for an example of SAS procedure). This model estimates a single within-household correlation coefficient. The model will include the fixed category effects of treatment group (placebo versus REGN10933+REGN10987), region (US versus ex-US), and age (≥ 12 to < 50 , ≥ 50 years). The model will use a compound symmetry covariance matrix and estimate the odds ratio between the treatment groups and corresponding 95% CI and p-value.

If the GEE model fails to converge due to most households containing only a single study subject in seronegative mFAS-A or the percentage of households in Cohort A with only a single study subject is 70% or more, then a logistic regression model will be used with treatment, region, and age group as fixed effects. The threshold of 70% was based on simulations of within-household correlation which show the type I error rate is inflated and the power is decreased when the

proportion of single-subject households is high (details provided in Section 6.6). If the logistic regression model does not converge, an exact logistic regression will be used. The estimates of odds ratio, the corresponding 95% CI and p-value will be provided from logistic regression (or exact logistic regression) for comparison of REGN10933+REGN10987 against placebo group.

In Cohort A, a subject will be considered having a symptomatic RT-qPCR confirmed SARS-CoV-2 infection (broad-term) during the EAP if any of the post-baseline RT-qPCR results during the EAP are positive with at least one symptom within 14 days of a positive RT-qPCR result (Section 4.5).

Cohort B

The Cohort B primary efficacy endpoint described in Section 4.5.5 will be analyzed in the seronegative mFAS-B population. The same statistical methods as described for Cohort A will be used to obtain the estimate of odds ratio and p-value for comparison between the treatment groups.

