6.6. Statistical Technical Issues

To consider the potential impact that not all of study subjects come from a household with more than one member participating this trial, a simulation has been conducted to explore the potential impact to the type I error rate and power by the percent of households with a single study subject only.

This simulation is based on the same sample size of 1248 (See [Table 1](#) in Section 2.2.1) assuming the attack rates are 10% and 5% in placebo and REGN10933+REGN10987 treatment group, respectively. The correlated Bernoulli response data (e.g. 1=infected vs 0=not infected) within a household was generated by using Gaussian multivariate cumulative distribution function proposed by Emrich and Piedmonte (1991). For example, the table below exhibits the correlation between the bivariate normal data with correlation ρ used to generate the Bernoulli correlated data and the corresponding Bernoulli correlation γ in the cases where the attack rates are both 10% (e.g., $p_1 = p_2 = 0.1$ under the null hypothesis), and 10% and 5% (e.g., $p_1 = 0.1, p_2 = 0.05$ under the alternative hypothesis).

$p_1 = p_2 = 0.1$		$p_1 = 0.1, p_2 = 0.05$	
ρ Normal	γ Bernoulli	ρ Normal	γ Bernoulli
0.1	0.03706	0.1	0.03065
0.2	0.07996	0.2	0.06748
0.3	0.12907	0.3	0.11089
0.4	0.18504	0.4	0.16150
0.5	0.24891	0.5	0.22020
0.6	0.32242	0.6	0.28834
0.7	0.40866	0.7	0.36813
0.8	0.51381	0.8	0.46328
0.9	0.65405	0.9	0.58016

Given the percent of subjects from households with single study subject (HHS), the rest of household size was randomly generated by using a truncated Poisson ($l = 4$) (i.e., resampling if ≤ 1). The simulation is repeatedly 2000 times by different HHS to compare the power between GEE model and logistic regression model based on boundary p-value=0.044 after 2 planned interim analyses.

Summary of power and type I error rate between the GEE model and logistic regression model by different HHS, considering the extreme high correlated data. The power is based on the testing p-value compared to the boundary p-value of 0.044 after 2 interim analyses at 50% and 75% information fraction for the final analysis.

Comparisons of Power

$\gamma = 0.58 (p_1 = 0.1, p_2 = 0.05)$		
HHS(%)	power-GEE	power-Logistic
10	0.9920	0.9035
20	0.9905	0.9040
30	0.9855	0.9140

Comparisons of Type I Error

$\gamma = 0.65 (p_1 = 0.1, p_2 = 0.1)$		
HHS(%)	α -GEE	α -Logistic
10	0.0480	0.0435
20	0.0490	0.0440
30	0.0495	0.0475

40	0.9590	0.8980
50	0.9245	0.9075
60	0.9035	0.9085

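### The sixth cohort A key secondary uses a subject-level Fisher's exact test although the compared exposure is the same for everyone in a household, so its 5% level is not guaranteed

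*SAP*

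**What the plan says.** SAP 5.7.3 and protocol 11.4.3.2 give the same rule for this endpoint: "the key binary endpoint regarding the index case linkage to R10933-10987-COV-2067, the Fisher's exact test will be used". Neither adds a household term. The endpoint is sixth in SAP Table 2, described there as a "comparison of those whose index cases receive REGN10933+REGN10987 vs placebo in R10933-10987-COV-2067", and it uses only this study's placebo group. For the whole sequence SAP 5.7.2 states: "The overall type I error will be controlled in each of seronegative mFAS-A and seronegative mFAS-B independently at 2-sided 5% significance level".

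Protocol 3.2.2 says that where two people are the first known cases together, "1 index case should be chosen, at the discretion of the investigator, to be labeled" as the index case. Randomisation in this study is by individual (SAP 2.1), so one household can supply several placebo contacts.

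For the primary endpoint, SAP 5.7.1 uses GEE with household as the cluster, and gives the reason: "In order to account for the correlation among subjects within a household and control the associated type 1 error inflation".

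**The concern.** The compared exposure is the arm of the labelled index case, so it does not vary within a household. If infections cluster in households, contacts in the same household carry partly the same information, and a test that counts each as independent understates the variance.

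If the earlier null hypotheses are false, this test is reached at the full 0.05, and the claim of overall control then rests on its own level. The endpoint carries a separate message: that treating the infected member protects untreated household contacts. Some secondary results may go into a submission dossier (protocol 11.4.9, SAP 7).

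**Working it through.** **Inputs from the documents.** Two-sided 0.05 (SAP 5.7.2). Household size: "assuming an average household size of 2.9 seronegative subjects", which is 1248/430 = 2.90. 1:1 individual randomisation (SAP 2.1). Correlation: SAP 2.2.1 says "the number of subjects per household, the correlation between subjects and symptomatic infection rates within a household are unknown", and its Table 1 explores 0.1 to 0.6. Infection rate: 10%, a proxy from the 10.3% of placebo subjects infected at day 8 in the administrative assessment (protocol 3.2.6). Those subjects are outside the analysis set (SAP 3.1).

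**Not in the documents.** The number of linked contacts or households, and 2067's allocation ratio. SAP 2.1 says only that some index cases may be in 2067.

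**The plan's own figures.** None exists for this endpoint beyond the 0.05 level. The household model behind SAP Table 1 was reproduced as a check. Simulated GEE power at correlation 0.1 to 0.6 was 0.928, 0.950, 0.956, 0.970, 0.985, 0.996, against the stated 0.914, 0.934, 0.956, 0.972, 0.983, 0.999. The odds ratio is (0.05/0.95)/(0.10/0.90) = 0.474 (stated 0.47). Enrolment is 1248/(0.9 × 0.7) = 1981 (stated 1980).

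**Placebo contacts per household (assumed shape).** Take household size as 1 + Poisson(1.9), with each member on placebo with probability 0.5. The mean is 2.9 × 0.5 = 1.45. Among households with at least one placebo contact it is 1.45/(1 − 0.5e^(−0.95)) = 1.45/0.807 = 1.80, and 47% of these hold exactly one.

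**Analytic check.** Design effect = 1 + (m − 1)ρ, with size-weighted m = 2.27. True level of a nominal 5% test = 2Φ(−1.96/√design effect).
- ρ = 0.1: 1.127, level 6.5%
- ρ = 0.3: 1.381, level 9.5%
- ρ = 0.6: 1.762, level 14%

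Fisher's conservatism lowers these, so simulation is needed.

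**Simulation A.** Fisher type I error (%), beta-binomial outcome, index arm assigned by household 1:1, 10% rate. There were 10,000 runs per cell for 60 or more contacts and 4,000 below that.

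| Linked contacts | ρ=0 | 0.1 | 0.2 | 0.3 | 0.6 |
|---|---|---|---|---|---|
| 20 | – | 0.9 | 0.9 | 1.6 | 3.1 |
| 30 | – | 1.8 | 2.0 | 2.8 | 4.6 |
| 40 | – | 2.1 | 3.7 | 3.6 | 5.5 |
| 60 | 2.4 | 3.5 | 4.1 | 5.0 | 8.4 |
| 120 | 3.3 | 4.3 | 5.8 | 6.8 | 11.3 |
| 200 | 3.6 | 4.3 | 6.4 | 7.5 | 11.3 |

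The 0.6 column is near the 0.58-0.65 that SAP 6.6 describes as "considering the extreme high correlated data".

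**Sensitivities** (120/200 contacts, %):

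| Change | ρ=0.1 | 0.3 | 0.6 |
|---|---|---|---|
| 5% rate | 3.0/4.4 | 5.1/6.5 | 7.9/9.9 |
| 15% rate | 4.4/5.3 | 7.6/7.9 | 11.4/12.0 |
| 2:1 allocation in 2067 | 4.1/4.6 | 6.7/7.5 | 9.7/11.4 |
| 70% of households with one study subject, rest of size 2-4 | – | 4.7/5.5 | 6.7/6.6 |
| 70% with one study subject, rest truncated Poisson(4) as in SAP 6.6 | – | 6.9/7.2 | 10.5/11.1 |

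The 2:1 case is an assumption, prompted by the two active IV doses in protocol 3.2.1. With 90% of linked households holding a single placebo contact, the level is 2.5-4.9%.

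**Simulation B** used a thresholded Gaussian outcome and 50 to 400 linked households. Fisher's level was 3.7-5.5% at ρ = 0.1, 5.7-8.7% at 0.3 and 9.7-13.6% at 0.65, rising to 18.8% with SAP 6.6's truncated Poisson(4) sizes. The top of that range would need almost all of the 430 planned households to be linked. With exposure randomised within households it stayed at 3.6-4.2%, so the household-constant exposure is what drives the inflation.

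**The case against.** The inflation needs three things together: a fair number of linked contacts, several placebo contacts per household, and correlation of about 0.2 to 0.3 or more. The documents establish none of these. At 40 or fewer linked contacts Fisher stays below 5% up to correlation 0.3, and with 70% single-subject households and the rest of size 2-4 it is close to nominal. All of this stands. It is why the size of the error cannot be stated for this trial.

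The parallel with the primary analysis is also limited. There, treatment varies within households, and SAP 6.6 shows logistic regression with no household term holding 3.6-4.9% at correlation 0.65. That is correct, so the point rests on the household-constant exposure and not on the analogy. For the same reason, SAP 6.6 gives no reassurance about this endpoint.

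The practical consequence is modest. The test is last, is reached only if the primary and five key secondaries succeed, and has low power: simulated power for true rates of 10% versus 5% at 120 to 200 contacts is 13-26%. A household may also contain more than one first-known case, so true exposure can be mixed. The grouping still follows the one labelled case.

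**Conclusion.** The concern holds. That the planned test ignores the unit at which the exposure varies is certain from the text. The size of the resulting error is conditional. For 20 to 200 linked contacts it runs from no inflation, to about 7-8% at correlation 0.3 with the planning household size, to 11-12% only near the correlations the SAP itself calls extreme. These figures rest on the assumed household mix, the 10% proxy rate (5% and 15% also tried), 1:1 or 2:1 allocation in 2067, and assumed linked numbers. They are a range, not an estimate for this trial.

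This should be corrected before the first-step lock, but it does not threaten the primary result or the other five key secondaries.

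**What to change.** In SAP 5.7.3 and protocol 11.4.3.2, replace Fisher's exact test for this endpoint with a permutation test that permutes the index-case arm by household, following the allocation 2067 actually used (ratio, strata, any change over time). State that it applies whatever the share of single-subject households, since the 70% rule in SAP 5.7.1 was set for the primary. Report linked households and linked contacts per arm. SAP 4.5.2 codes this endpoint as continuous while 5.7.3 calls it binary; correct that too. SAP 5.7.4 uses Fisher's test for similar linkage endpoints outside alpha control, and the same change would suit them.

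The permutation test held 4.1-5.1% in simulation A (60 to 200 contacts, 1:1 and 2:1) and 4.4-5.6% in simulation B. A logistic GEE clustered on household with robust errors is an alternative only with about 120 or more linked contacts: in simulation A at 1:1 it gave 3.5-5.6% at 120-200, but only 1.5-1.8% at 60.

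The cost is a wording change and a short program, as household identifiers are already assigned. Power, permutation versus Fisher:
- 10% vs 5%, ρ = 0.1: 15% vs 14% (120 contacts), 24% vs 23% (200)
- 10% vs 5%, ρ = 0.3: 13% vs 16% (120), 21% vs 26% (200)
- 10% vs 2%, 200 contacts: 64% vs 62% (ρ = 0.1), 58% vs 62% (ρ = 0.3)

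Part of Fisher's apparent advantage at 0.3 is its inflated level.
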